8.1.2. Tables over the whole 24 weeks period

Tables will present Weeks 1-2-4-8-12-16-20-24, unless specified otherwise. Tables will present the imputed 4 treatment groups up to Week 12, and leave out the placebo group after Week 12, as mentioned in section 2.1.1.

Table 14.2.1.1.1: ACR20: Summary with overall p-value and pairwise comparisons versus placebo

Logistic regression model at each time point, modeling the responders. Factors in the model are: treatment, region, and previous use of biologics.

Per time point, the table will present:

- Overall type-III p-value for all explanatory factors in the model.
- Per group: number and percentage of responders, difference in percentage responders versus the placebo group (GLPG0634 minus placebo), together with a 95% confidence interval of this difference (as provided by SAS PROC FREQ).
- Per group: p-value for pairwise comparison versus the placebo group, derived from contrasts within the overall regression model. These p-values will be presented both as uncorrected p-values as well as corrected for multiplicity according to Hommel's closed-testing method (SAS PROC MULTTEST).

The "raw" SAS PROC output must be provided in a statistical appendix listing.

The table will show:

- NRI in ITT and in per-protocol
- LOCF in ITT and in per-protocol
- observed-case in ITT (descriptive at Week 12 + 24; inferential statistics at Week 12 only).

Table to be created for the Week 12 interim analysis as well, cut off at Week 12. ITT only.

Table 14.2.1.1.2: ACR20: Exploratory pairwise comparisons among the dose groups

Logistic regression model at each time point, modeling the responders. Factors in the model are: treatment, region, and previous use of biologics.

Per time point, the table will present:

- Per group: difference in percentage responders versus the other GLPG0634 groups, together with a 95% confidence interval of this difference (as provided by SAS PROC FREQ).
- Per group: p-value for pairwise comparison versus the other GLPG0634 groups. These p-values will be presented both as uncorrected p-values, and are derived as contrasts within the overall logistic regression model. As this is a purely exploratory analysis, no adjustment for multiplicity will be performed.

The "raw" SAS PROC output must be provided in a statistical appendix listing.

The table will show:

- NRI in ITT and in per-protocol
- LOCF in ITT and in per-protocol
- observed-case in ITT (inferential statistics at Week 12 only).

Table to be created for the Week 12 interim analysis as well, cut off at Week 12. ITT only.

Table 14.2.1.1.3: ACR50: Summary with overall p-value and pairwise comparisons versus placebo

Repeat table of the ACR20 table.

The table will show:

- NRI in ITT

- LOCF in ITT
- observed-case in ITT (descriptive at Week 12 + 24; inferential statistics at Week 12 only).

Table to be created for the Week 12 interim analysis as well, cut off at Week 12.

Table 14.2.1.1.4: ACR50: Exploratory pairwise comparisons among the dose groups

Repeat table of the ACR20 table.

The table will show:

- NRI in ITT
- LOCF in ITT
- observed-case in ITT (inferential statistics at Week 12 only).

Table to be created for the Week 12 interim analysis as well, cut off at Week 12.

Table 14.2.1.1.5: ACR70: Summary with overall p-value and pairwise comparisons versus placebo

Repeat table of the ACR20 table.

The table will show:

- NRI in ITT
- LOCF in ITT
- observed-case in ITT (descriptive at Week 12 + 24; inferential statistics at Week 12 only).

Table to be created for the Week 12 interim analysis as well, cut off at Week 12.

Table 14.2.1.1.6: ACR70: Exploratory pairwise comparisons among the dose groups

Repeat table of the ACR20 table.

The table will show:

- NRI in ITT
- LOCF in ITT
- observed-case in ITT (inferential statistics at Week 12 only).

Table to be created for the Week 12 interim analysis as well, cut off at Week 12.

Table 14.2.1.1.7: ACR20 at Week 12: Tabulation versus baseline characteristics

The table will show two methods of imputing missing values: LOCF and NRI.

Frequency tabulation of the ACR20 response rate at Week 12 per treatment group, split up according to the following baseline categories:

- Demographics:
 - Region (as used in the central randomization)

- Country
- Gender
- Age categories:
 - < 45 ;
 - [45,65[;
 - [65,75[;
 - ≥ 75 years
- BMI categories:
 - ≤ 18.5;
 -] 18.5 , 25.0] ;
 -] 25 , 30 [,
 - ≥ 30 kg/m²
- Baseline disease characteristics:
 - Duration of RA:
 - < 1;
 - [1 , 2 [;
 - [2 , 5 [;
 - [5 , 10 [;
 - [10 , 20 [;
 - ≥ 20 years
 - Baseline CRP:
 - <0.7 x ULN;
 - [0.7,1.0] x ULN;
 -]1.0,1.2[x ULN;
 - ≥ 1.2 x ULN
 - Baseline TJC68: < 20, ≥ 20
 - Baseline SJC66: < 20, ≥ 20
 - Baseline DAS28(CRP): high, moderate, low, remission (see further section on DAS28 for the definition of these categories)
 - RF status
 - Anti-CCP status
 - Previous use of:
 - Biological DMARD (anti-TNF or other biological DMARD) yes/no,
 - anti-TNF yes/no,
 - other biological DMARD yes/no,
 - conventional DMARD yes/no,
 - NSAID yes/no,
 - steroid yes/no,
 - analgesic yes/no,
 - other RA medication yes/no.

Population: ITT.

Table to be created for the Week 12 interim analysis as well.

Table 14.2.1.1.8: ACR20 at Week 12: Exploratory logistic regression model containing baseline characteristics

The table will show two methods of imputing missing values: LOCF and NRI.

Logistic regression model of the ACR20 response at Week 12, with the following exploratory factors:

- Treatment group
- Demographics:
 - Region
 - Country
 - Gender
 - Age as continuous variable
 - BMI as continuous variable
- Baseline disease characteristics:
 - Duration of RA as continuous variable
 - Baseline CRP as continuous variable
 - Baseline TJC68 and SJC66 as continuous variables
 - Baseline DAS28(CRP) as continuous variable
 - RF status
 - anti-CCP status
 - Previous use of:
 - Biological DMARD (anti-TNF or other biological DMARD) yes/no,
 - anti-TNF yes/no,
 - other biological DMARD yes/no,
 - conventional DMARD yes/no,
 - NSAID yes/no,
 - steroid yes/no,
 - analgesic yes/no,
 - other RA medication yes/no.

All these factors will be tested using a stepwise selection approach. Significance level to enter the model: 0.10; significance level to stay in the model: 0.05. The treatment groups will always be kept in the model, even when not significant at level 0.05. The table will present only the final model with type-III p-value and odds ratio estimates. The “raw” SAS PROC output must be provided in a statistical appendix listing, and will contain all details on the model building steps.

Population: ITT.

Table 14.2.1.1.9: ACR-N: Summary with overall p-value and pairwise comparisons versus placebo

P-values are generated from an ANOVA model at each time point. Factors in the model are: treatment, region, and previous use of biologics.

Per time point, the table will present:

- Per group: sample regular statistics.

- Per group: difference in LS-means versus the placebo group (GLPG0634 minus placebo), together with a 95% confidence interval of this difference.
- Overall type-III p-value for “treatment”.
- Per group: p-value for pairwise comparison versus the placebo group, derived from contrasts within the overall model. These p-values will be presented both as uncorrected p-values as well as corrected for multiplicity according to Hommel’s closed-testing method (SAS PROC MULTTEST).

Frequency per time point (weeks 12 and 24 only), and per treatment group. ACR-N will be presented in the following categories:

<10,
[10,20[,
[20,30[,
[30,40[,
[40,50[,
[50,60[,
[60,70[,
[70,80[,
[80,90[,
[90,100].

The “raw” SAS PROC output must be provided in a statistical appendix listing.

The table will show:

- LOCF in ITT
- observed-case in ITT (descriptive at week 12 + 24; inferential statistics at Week 12 only).

Table to be created for the Week 12 interim analysis as well, cut off at Week 12.

Table 14.2.1.1.10: ACR-N: Exploratory pairwise comparisons among the dose groups

ANOVA model at each time point. Factors in the model are: treatment, region, and previous use of biologics.

Per time point, the table will present:

- Per group: difference in LS-means versus the other GLPG0634 groups, together with a 95% confidence interval of this difference.
- Per group: p-value for pairwise comparison versus the other GLPG0634 groups. These p-values will be presented both as uncorrected p-values, and are derived as contrasts within the overall model. As this is a purely exploratory analysis, no adjustment for multiplicity will be performed.

The “raw” SAS PROC output must be provided in a statistical appendix listing.

The table will show:

- LOCF in ITT
- observed-case in ITT (inferential statistics at Week 12 only).

Table to be created for the Week 12 interim analysis as well, cut off at Week 12.

Table 14.2.1.1.11: Time to ACR20 response: Descriptive statistics and between-group comparison

Descriptive statistics per treatment group.

Between-group comparison (overall and all pairwise comparisons versus placebo)

P-values are generated from a Cox proportional hazards regression model. Factors in the model are: treatment, region, and previous use of biologics.

The table will present:

- Per group: N (number of events, number of censored, number in total), mean (SE), median, quartiles.
- Overall type-III p-values for treatment, region and previous use of biologics.
- Per group: p-value for pairwise comparison versus the placebo group. These p-values will be corrected for multiplicity according to Hommel's closed-testing method as implemented in SAS PROC MULTTEST. The uncorrected p-values will also be presented.

A frequency table of the time-to-event in categories (Week 1, Week 2, Week 4, Week 8, Week 12, never) will also be presented.

The "raw" SAS PROC output must be provided in a statistical appendix listing.

Population: ITT.

Table 14.2.1.1.12: Time to ACR20 response: Exploratory pairwise comparisons among the dose groups

Cox proportional hazards regression model. Factors in the model are: treatment, region, and previous use of biologics.

The table will present per group: p-value for pairwise comparison versus the other GLPG0634 groups. These p-values will be presented both as uncorrected p-values, and are derived as contrasts within the overall model. As this is a purely exploratory analysis, no adjustment for multiplicity will be performed.

The "raw" SAS PROC output must be provided in a statistical appendix listing.

Population: ITT.

Table 14.2.1.1.13: Time to ACR50 response: Descriptive statistics and between-group comparison

Repeat table of the ACR20 table.

Population: ITT.

Table 14.2.1.1.14: Time to ACR50 response: Exploratory pairwise comparisons among the dose groups

Repeat table of the ACR20 table.

Population: ITT.

Table 14.2.1.1.15: Time to ACR70 response: Descriptive statistics and between-group comparison

Repeat table of the ACR20 table.

Population: ITT.

Table 14.2.1.1.16: Time to ACR70 response: Exploratory pairwise comparisons among the dose groups

Repeat table of the ACR20 table.

Population: ITT.

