This study is not powered for any formal comparison among the dose groups. However, differences among the q.d. groups will be calculated and presented with a 95% confidence interval (all time points, also after Week 12). No adjustment for multiplicity will be done for these exploratory differences.

Analysis methods per post-baseline time point:

- Binary parameters (such as ACR20): logistic regression model with factors treatment, region and previous use of biologics.
- Continuous parameters: both the changes from baseline and the percent changes from baseline will be described. Formal between-group comparisons will be performed on the changes from baseline only, using an analysis of (co)variance (AN[C]OVA) model with factors treatment, baseline value, region and previous use of biologics. Baseline will be the last nonmissing value prior to first dosing in the study.
- Time to (first) response (ACR20/50/70) will be analyzed using Kaplan-Meier survival techniques, and groups will be compared against placebo using a Cox proportional hazards regression model with factors treatment, region and previous use of biologics.

Quality of Life data (FACIT fatigue scale and SF-36 questionnaire) will be analyzed descriptively. Exploratory between-group comparisons will also be done at each post-baseline time point using AN(C)OVA models on the changes from baseline with factors treatment, baseline value, region and previous use of biologics.

A descriptive sensitivity analysis by baseline characteristic (such as country, geographic region, previous use of biological DMARDs etc) will be performed for the ACR20 response and the change in DAS28(CRP). Additionally an exploratory regression model will be fitted using a stepwise selection algorithm on the ACR20 response and the change in DAS28(CRP) at Week 12, using treatment and baseline characteristics as explanatory factors to investigate which baseline factors have an influence on the response.

Graphical presentations are added to facilitate the overall interpretation of the study results.

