7.1. SUBJECT DISPOSITION

Listing 16.2.1.1: Subject disposition: Randomization

Listing of subject numbers, randomization and re-randomization groups, population flags, any information on code breaking, stratification factors (region, previous use of biologics), country and site.

All discrepancies (as-randomized versus as-treated, or discrepancies in stratification factors) will be flagged.

Regions used in the central randomization in the DARWIN program are:

Region	Countries belonging to the region
1: Latin America	Argentina, Chile, Colombia, Guatemala, Mexico
2: Central and Eastern Europe, EU	Bulgaria, Hungary, Latvia, Poland, Romania
3: Central and Eastern Europe, non-EU	Russia, Ukraine, Moldova
4: West and Asia Pac	Australia, Austria, Czech Republic, Germany, New Zealand, Spain, USA

Population: all randomized population.

Listing 16.2.1.2: Subject disposition: Region, country and site identification

Listing of region, country and site numeric codes used for the numbering of the subjects, and the meaning of these codes.

Population: all screened population.

Table 14.1.1.1: Subject disposition: Tabulation by region, country and investigator

Tabulation per initial treatment group (and overall) of the number of subjects in each of the regions, countries and investigator sites. For the interim analysis, only regions and countries will be presented.

Population: all randomized.

Table to be created for the Week 12 interim analysis as well.

Table 14.1.1.2: Subject disposition: Analysis populations

Tabulation per initial treatment group (and overall) of the number of subjects in each of the analysis populations defined in section 3.1, separated per study period.

Population: all screened population.

Table 14.1.1.3: Subject disposition: No-treatment subjects: Tabulation of the reasons

Tabulation of discontinuations and the reasons for discontinuation.

Population: all screened population, minus the safety population (so selecting only subjects who were never exposed to the study medication: subjects either never randomized or randomized but not exposed).

Table 14.1.1.4: Subject disposition up to Week 12: Tabulation of the number of subject at each time interval

Tabulation per treatment group (and overall) and per time point (up to and including Week 12).

Population: safety.

Table 14.1.1.5: Subject disposition up to study end: Tabulation of the number of subject at each time interval

Repeat table after Week 12 and follow-up.

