 - ≥ 1.2 x ULN
 - Baseline TJC68: < 20, ≥ 20
 - Baseline SJC66: < 20, ≥ 20
 - Baseline DAS28(CRP): high, moderate, low, remission (see further section on DAS28 for the definition of these categories)
 - RF status
 - Anti-CCP status
 - Previous use of:
 - Biological DMARD (anti-TNF or other biological DMARD) yes/no
 - anti-TNF yes/no,
 - other biological DMARD yes/no,
 - conventional DMARD yes/no,
 - NSAID yes/no,
 - steroid yes/no,
 - analgesic yes/no,
 - other RA medication yes/no.

Population: ITT.

Table 14.2.1.4.7: DAS28(CRP) change from baseline at Week 12: Exploratory ANCOVA model containing baseline characteristics

The table will show LOCF only.

ANCOVA model of the DAS28(CRP) change from baseline at Week 12, with the following exploratory factors:

- Treatment group
- Demographics:
 - Region
 - Country
 - Gender
 - Age as continuous variable
 - BMI as continuous variable
- Baseline disease characteristics:
 - Duration of RA as continuous variable
 - Baseline CRP as continuous variable
 - Baseline TJC68 and SJC66 as continuous variables
 - Baseline DAS28(CRP) as continuous variable
 - RF status
 - anti-CCP status
 - Previous use of:
 - Biological DMARD (anti-TNF or other biological DMARD) yes/no
 - anti-TNF yes/no,
 - other biological DMARD yes/no,
 - conventional DMARD yes/no,
 - NSAID yes/no,
 - steroid yes/no,
 - analgesic yes/no,
 - other RA medication yes/no.

All these factors will be tested using a stepwise selection approach. Significance level to enter the model: 0.10; significance level to stay in the model: 0.05. The treatment groups will always be kept in the model, even when not significant at level 0.05. The table will present only the final model with type-III p-value and LS-mean estimates. The “raw” SAS PROC output must be provided in a statistical appendix listing, and will contain all details on the model building steps.

Population: ITT.

Table 14.2.1.4.8: DAS28(CRP) remission: Summary with overall p-value and pairwise comparisons versus placebo

Similar table as for ACR20, presenting the rates of DAS28(CRP) remission at Week 12 and Week 24.

The table will show:

- NRI in ITT
- LOCF in ITT
- observed-case in ITT (descriptive at Week 12 + 24; inferential statistics at Week 12 only).

Table 14.2.1.4.9: DAS28(CRP) remission: Exploratory pairwise comparisons among the dose groups

Table 14.2.1.4.10: DAS28(CRP) remission and low disease activity: Summary with overall p-value and pairwise comparisons versus placebo

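### The exploratory stepwise tables keep at least one baseline factor in roughly 54-64% of trials where none matters, so a lone selected factor with p just under 0.05 is weak evidence

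*SAP*

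**What the plan says.** SAP section 6.1.2.3 plans an exploratory regression on ACR20 response and on the DAS28(CRP) change at Week 12. Its purpose is "to investigate which baseline factors have an influence on the response".

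Section 8.1.2, Table 14.2.1.1.8, gives the detail for ACR20. Besides treatment it lists 20 candidates:
- five demographic: region, country, gender, age, BMI;
- seven disease-related: RA duration, CRP, TJC68, SJC66, DAS28(CRP), RF status, anti-CCP status;
- eight yes/no items on previous treatment.

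All of them are to be "tested using a stepwise selection approach. Significance level to enter the model: 0.10; significance level to stay in the model: 0.05". Only treatment is protected: "The treatment groups will always be kept in the model, even when not significant at level 0.05". The search is run under both LOCF and NRI. The table shows the final model with type-III p-values and odds ratios; the selection steps go to an appendix listing.

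Section 8.4.2, Table 14.2.1.4.7, repeats the rule for DAS28(CRP), under LOCF: "The table will present only the final model with type-III p-value and LS-mean estimates". Neither section makes any allowance for the search.

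**The concern.** A factor's appearance in the final table will be read as an answer to the question in section 6.1.2.3. The table shows the survivors and their p-values but not the candidates that failed, so a reader of the table alone cannot see how wide the search was. Surviving estimates are conditional on having passed a significance threshold, which pushes them away from no effect.

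The candidate list also overlaps with itself.
- Section 7.1 ("Regions used in the central randomization in the DARWIN program are") assigns every country to one region, so country determines region.
- The biological DMARD item is defined as the union of two other candidates.
- Conventional DMARD use is constant if prior MTX counts as one, because Protocol section 8.3.2, criterion 5, requires an inadequate response to MTX. The coding is not shown.
- Region and previous biologic use are in the primary model, yet this rule may drop them.

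In the DAS28(CRP) table, LS-means give no effect estimate for the seven continuous candidates. At stake is how these tables are interpreted, not the trial's main conclusion.

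**Working it through.** **Plan's own figure.** The documents state no false-selection rate, so there is none to reproduce. As a check on the design inputs, a two-sided two-proportion power calculation with n = 70 per arm and alpha = 0.05/3 (Protocol section 8.8.2) gives:
- 43% v 15%: 90.7%, and 70% v 40%: 89.1% (stated 90%);
- 39% v 15%: 79.8%, and 67% v 40%: 80.0% (stated 80%).

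**Inputs from the documents.** Entry 0.10, stay 0.05, treatment forced in, 5 + 7 + 8 = 20 candidates, N = 280, placebo response 15% to 40%.

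**Simple calculation.** A factor entering with p between 0.05 and 0.10 is removed again at the stay step, so the false-retention rate is about 0.05 per factor. For k independent null factors, P(at least one kept) = 1 - 0.95^k:
- k = 20: 64.2%.
- k = 17: 58.2%. This is 20 less country (which determines region), the composite and the constant item.

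The 0.10 entry level alone would give 1 - 0.90^20 = 87.8%, so the stay level drives the result.

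**Simulation of the rule itself.** Score test to enter, Wald test to stay, 4 x 70 subjects, treatment effects present, no baseline factor prognostic. Response rates were 15/43/43/43% or 40/55/60/70%; the 55% and 60% are assumed.
- 20 independent factors: at least one kept in 62-63%; mean about 1.0 kept; two or more in about 27%.
- Listed overlaps built in, prior biologic use assumed at 5%, 10% or 20%: at least one kept in 54-57% (Monte Carlo SE 1.3 points); mean about 0.8; two or more in about 19-20%.

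Prevalences, correlations and country mix are assumptions. The DAS28(CRP) search was not simulated; the same per-factor arithmetic applies to it.

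**Size of the distortion.** Take 15/43/43/43%, so overall response is (15 + 3 x 43)/4 = 36%. Ignoring adjustment, the SE of a log odds ratio per SD is about 1/sqrt(280 x 0.36 x 0.64) = 0.1245. To reach p = 0.05, a null continuous factor must show an odds ratio of at least exp(1.96 x 0.1245) = 1.28 per SD, or its inverse. In simulation, selected noise factors averaged about 1.4 per SD, or its inverse.

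**Discrimination.** One real continuous factor added, overlapping candidates, prior biologic use 10%:

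| True OR per SD | Real factor selected | Any noise factor also kept |
|---|---|---|
| 1.3 | 55% | 51% |
| 1.5 | 87% | 49% |
| 2.0 | 100% | 53% |

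A given null factor is selected in about 4-5% of trials.

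**The alternative.** One model with 17 factors and Hommel adjustment names any false factor in about 4-6% of all-null trials, against 55-62% unadjusted. Its 95% CIs covered about 94% in simulation.

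**The case against.** The strongest reply is that the SAP does not oversell this analysis. Section 6.1.2.3 and the table titles call it exploratory. The SAP makes no multiplicity adjustment for its other exploratory comparisons. The primary model is fixed as treatment, region and previous biologics, and nothing selected here feeds it. The model-building steps are kept in the appendix. Tables 14.2.1.1.7 and 14.2.1.4.6 and the responder/non-responder Tables 14.1.3.2, 14.1.3.9 and 14.1.3.12 show baseline factors without selection. All of this stands, and it limits the point to interpretation. It does not remove the point, because those other tables are descriptive splits, one factor at a time, without mutually adjusted estimates.

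A reader might infer that the rule cannot tell real predictors from noise. The numbers do not support that: a factor with odds ratio 1.5 per SD is selected in about 85-87% of trials, a given null factor in about 5%. The 54-64% is the chance of any false selection when nothing matters. It is not the chance that a particular selected factor is false.

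A reader might also infer that these tables will steer phase III stratification or eligibility. The documents say no such thing; the phase III use they name is preliminary dose selection from the interim analysis, and Table 14.2.1.1.8 is not marked for it.

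Two objections to a full model have weight. First, it is large: region 3 + 16 other factors + treatment 3 = 22 parameters. The rarer outcome has about 101 subjects (10.5 + 3 x 30.1 at 15/43%) or 105 (42 + 3 x 21 at 40/70%), under 5 per parameter. CI coverage nevertheless held at about 94%. Second, making adjusted significance the only criterion would cost sensitivity: about 85% falls to 52% at odds ratio 1.5 per SD. That argues for showing both p-values, not for keeping the selected-only table. DAS28(CRP) beside its own components, and possibly sparse prior-biologic items, will widen some intervals.

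**Conclusion.** The point holds as a matter of interpretation and reporting. As specified, the search would keep at least one factor in roughly 54-64% of trials in which no baseline factor matters: the lower end with the overlaps simulated, the upper end if all 20 candidates were independent. Every scenario tried exceeded one half, but the exact figure rests on correlations, prevalences and country mix that the documents do not give. P-values and odds ratios of selected factors are too extreme, and a single one just under 0.05 is weak evidence. Strong predictors will still stand out, and the primary analysis is untouched. The change is worth making because it is cheap and serves the SAP's stated aim better.

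**What to change.** In Tables 14.2.1.1.8 and 14.2.1.4.7, replace the selected-only model, or accompany it, with one prespecified model.
- **Contents:** treatment, region and the other candidates. Leave out country (results by country remain in Tables 14.2.1.1.7 and 14.2.1.4.6), the biological DMARD composite and, if constant, conventional DMARD.
- **Reporting:** every factor's odds ratio, or regression coefficient for DAS28(CRP), with a 95% CI. Show unadjusted and Hommel-adjusted p-values side by side; PROC MULTTEST is already used for this in section 8.1.2.
- **Wording:** describe factors significant only before adjustment as hypothesis-generating.

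The cost is SAP text, one model call per table and slightly more output. Weak predictors will often miss adjusted significance: for one binary factor, power is about 76% adjusted against 95% unadjusted at odds ratio 2.5, and 44% against 79% at odds ratio 2. Their estimates and intervals stay in the table.
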